Official Title: Three-Dimensional Computed Tomography Assessment of Arcuate Foramen Variants and Their Surgical Implications: A Retrospective Observational Study

NCT Number: [To be assigned after registration]

Document Date: August 11, 2025

1. Background and Rationale

The arcuate foramen (AF) is an anatomical variation of the atlas (C1 vertebra) resulting from ossification of the posterior atlanto-occipital membrane, forming a bony bridge over the vertebral artery groove. While frequently asymptomatic, AF has been associated with vertebrobasilar insufficiency, cervicogenic headache, and neck pain. Importantly, AF may increase the risk of vertebral artery or suboccipital nerve injury during craniocervical junction surgery. This study aims to determine the prevalence and types of AF in a Turkish population using high-resolution three-dimensional computed tomography (3D CT) and to evaluate its potential surgical implications.

2. Objectives

Primary Objective: To determine the prevalence of complete and incomplete AF variants using 3D CT.

Secondary Objectives: (1) To assess the association between AF presence and demographic variables; (2) To evaluate interobserver agreement in AF detection.

3. Study Design

This is a retrospective, cross-sectional observational study conducted at Giresun University Faculty of Medicine. The study population includes adult patients who underwent head CT or CTA between January 2023 and July 2025.

4. Methods

Inclusion Criteria: Age \geq 18 years; high-quality CT or CTA images including atlas vertebra; complete demographic data. **Exclusion Criteria:** Significant motion or metallic artifact; prior cervical surgery or trauma; congenital anomalies obscuring anatomy. **Imaging Technique:** All scans were acquired using FUJIFILM SUPRIA CT system and reconstructed using OsiriX MD software with a 3D volume rendering technique. **AF Classification:** Complete (full bony ring) or incomplete (partial bony projection), further categorized by side (right, left, bilateral).

5. Outcome Measures

Primary Outcome: Prevalence of complete and incomplete AF with 95% confidence intervals.

Secondary Outcomes: Association between AF and age/sex; interobserver agreement measured by Cohen's Kappa.

6. Statistical Analysis Plan

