Descriptive statistics will summarize continuous variables as mean \pm standard deviation and categorical variables as frequencies and percentages. Chi-square or Fisher's exact test will be used for categorical comparisons, and independent t-test for continuous variables. Interobserver agreement will be calculated using Cohen's Kappa. A p-value < 0.05 will be considered statistically significant. Post-hoc power analysis indicated a study power of 83% with 200 participants for an expected prevalence of 15% ($\alpha = 0.05$).

7. Ethics and Regulatory Compliance

The study protocol was approved by the Giresun University Faculty of Medicine Ethics Committee (Approval No: E-53593568-771-250207806, Date: July 31, 2024). All data were de-identified prior to analysis in compliance with relevant data protection regulations.

8. References

3. Arslan D, Özer MA, Govsa F, Kiti Ö. World Neurosurg. 2018;113:e579–e585.
5. Keser N, Çakla U, Özaydin B, et al. Istanbul Med J. 2019;20(5):377-381.

Study Protocol and Statistical Analysis Plan - Summary

Study Protocol

Official Title: Three-Dimensional Computed Tomography Assessment of Arcuate Foramen Variants and Their Surgical Implications: A Retrospective Observational Study

Background and Rationale: The arcuate foramen (AF) is an anatomical variation of the atlas (C1 vertebra) resulting from ossification of the posterior atlanto-occipital membrane, forming a bony bridge over the vertebral artery groove. While often asymptomatic, AF has been associated with vertebrobasilar insufficiency, cervicogenic headache, and neck pain. Importantly, AF may increase the risk of vertebral artery and suboccipital nerve injury during cranivertebral junction surgery.

Objectives: Primary Objective: To determine the prevalence of complete and incomplete AF variants using 3D CT. Secondary Objectives: (1) To assess the association between AF presence and demographic factors; (2) To evaluate interobserver agreement in AF detection.

Study Design: Retrospective, cross-sectional observational study conducted at Giresun University Faculty of Medicine. Data were collected from January 2023 to July 2025.

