Methods: Inclusion criteria: Age \geq 18 years; high-quality CT or CTA images including the atlas; complete demographic data. Exclusion criteria: Motion or metallic artifact; prior cervical surgery or trauma; congenital anomalies obscuring anatomy. Imaging was performed on a FUJIFILM SUPRIA CT system and reconstructed using OsiriX MD with 3D volume rendering. AF was classified as complete (full bony ring) or incomplete (partial bony projection) and categorized by side (right, left, bilateral).

Outcome Measures: Primary: Prevalence of complete and incomplete AF (95% CI). Secondary: Association with age/sex; interobserver agreement (Cohen's Kappa).

Statistical Analysis Plan

Descriptive statistics: Continuous variables as mean \pm standard deviation; categorical variables as frequencies and percentages. Chi-square or Fisher's exact test for categorical data; independent t-test for continuous data. Interobserver agreement assessed by Cohen's Kappa. Significance level set at $p < 0.05$. Post-hoc power analysis indicated 83% power with 200 participants for an expected prevalence of 15% ($\alpha = 0.05$).

Ethics Approval: Approved by the Giresun University Faculty of Medicine Ethics Committee (Approval No: E-53593568-771-250207806, Date: July 31, 2024). All data were de-identified before analysis.

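### The age/sex outcome is analysed only with two-variable tests, which describe crude associations but cannot separate sex from age; one joint logistic model would do so at little cost

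*Combined protocol and SAP*

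**What the plan says.** Section 2 sets a secondary objective, "To assess the association between AF presence and demographic variables", and Section 5 turns it into the outcome "Association between AF and age/sex". For comparisons, Section 6 names chi-square or Fisher for categorical variables and the t-test for continuous ones: "exact test will be used for categorical comparisons, and independent t-test for continuous variables". The Summary's analysis plan says the same: "exact test for categorical data; independent t-test for continuous data". In practice that means AF by sex in a two-by-two table, and mean age in patients with and without AF. The decision rule is "A p-value < 0.05 will be considered statistically significant".

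Neither version mentions regression, stratification, matching or standardisation. Section 3 describes a clinical imaging series: "The study population includes adult patients who underwent head CT or CTA between January 2023 and July 2025". Nothing in the eligibility criteria balances age between men and women. Section 4 does require "complete demographic data", so age and sex should be available for every patient.

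**The concern.** The plan asks about two demographic factors and tests each while ignoring the other. In a hospital CT series the sexes may differ in age. If they do, and if AF becomes more or less frequent with age, the sex comparison carries part of the age relation. It may then show a difference that disappears among people of the same age, or it may shrink a real one. The age comparison can likewise carry part of a sex relation. A confidence interval around the crude result would not help, because it would be an interval for the same mixed quantity.

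At stake is how the secondary result may be read. A crude p-value below 0.05 for sex could be reported as if sex mattered in its own right, and the planned analysis has no means of checking that.

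**Working it through.** **The plan's own figure.** Section 6 gives 83% power for 200 participants at 15% prevalence. It cannot be reproduced, because no null value, comparison or sidedness is stated. A two-sided one-sample test would need a null prevalence of about 8.7% or 23.3%. A comparison of 100 with 100 would need a difference between 14 points (about 80% power) and 16 points (about 89%). The present point does not depend on this figure.

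**Inputs from the documents.** n = 200, AF prevalence 15%, alpha 0.05. Expected AF cases: 200 x 0.15 = 30.

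**Assumed inputs, varied over a range.** 100 men and 100 women; age SD 16 years (17 in a second set of runs); age gap between the sexes 0 to 10 years; AF odds multiplied by 1.0 to 1.5 per decade of age.

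**Model.** logit P(AF) = b0 + ln(OR per decade) x age/10 + ln(OR for sex) x sex, with b0 set so that overall prevalence is 15%.

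**Hand approximation.** Crude sex OR ≈ true sex OR x (OR per decade)^(gap/10), with the gap taken as negative when the higher-risk sex is younger.

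**No true sex effect** (SD 16, 20,000 runs; rejection at p < 0.05):

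| Gap | Odds per decade | Hand approximation | Simulated crude OR | Chi-square rejects |
|---|---|---|---|---|
| 5 years | x1.2 | 1.2^0.5 = 1.10 | 1.09 | 5.6% |
| 8 years | x1.3 | 1.3^0.8 = 1.23 | 1.22 | 8% |
| 10 years | x1.3 | 1.3^1 = 1.30 | 1.29 | 9.5% |
| 10 years | x1.5 | 1.5^1 = 1.50 | 1.46 | 15.5% |

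The joint logistic model rejects in 5.1% to 5.4% in all four cases. A repeat with 6,000 runs per case gave 5.5%, 8.3%, 10.5% and 16.2% for chi-square, and 5.3% to 5.6% for the joint model.

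**When the distortion is absent** (SD 17, 2,000 runs). With no gap, chi-square rejects in 4.8% to 5.2%. With a gap of 5 or 10 years but no age gradient, it rejects in 5.4% and 5.8%. The simulation standard error is sqrt(0.05 x 0.95 / 2,000) = 0.5 points, and with no gradient AF does not depend on the age gap at all, so these are noise around 5%.

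**A true sex effect that is masked.** True sex OR 2.0, higher-risk sex 8 years younger, odds x1.4 per decade: hand approximation 2.0 x 1.4^(-0.8) = 1.53; simulated crude OR about 1.5. Chi-square power is 18%, against 38% for the joint model, which recovers an OR of 2.0. In a milder case (5-year opposing gap, x1.2 per decade) the powers are 32% and 40%.

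**The age test.** With no age effect, a true sex OR of 2.0 to 2.5 and a gap of 8 to 10 years, the t-test rejects in about 6% to 10%.

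**Feasibility.** 30 cases / 2 terms = 15 cases per term.

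**The case against.** The strongest reply is that the plan asks for an association and does not call it independent, adjusted or causal. Whether AF is more frequent in one sex among imaged adults is a legitimate descriptive question, and chi-square or Fisher answers it. A crude difference that partly reflects age is still a true difference in that sample. This stands: the gap lies in what the results can be used to say, and the tests themselves are not invalid.

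Second, the two conditions for distortion are not in the documents. A reader might infer an age gradient from Section 1, which attributes AF to ossification. That describes how the variant forms; it does not say that AF becomes more common after age 18, the entry threshold. No age difference between the sexes is reported either. This also stands.

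Third, the size is close to nil at modest inputs: 5.6% against a nominal 5% in the mildest case. The upper figure needs a 10-year gap and x1.5 per decade, which is 1.5^4 = 5.1 times the odds over 40 years. Even the joint model has only 38% power in the masking example, so it would still miss a true OR of 2.0 about 62% of the time. That is a sample-size limit which the model does not remove.

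A reader might also take age/sex to be the study's only inferential question. It is not: the primary outcome is prevalence with 95% confidence intervals, which is inference too.

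What the reply does not remove is that neither version of the plan can say whether a sex or age result is separate from the other factor, although both variables should be complete for every patient.

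**Conclusion.** The point holds in a limited form. The planned tests describe crude associations and cannot separate sex from age. If the sexes differ in age and AF varies with age, false rejection for sex would be about 6% to 16% over the assumed range, against about 5% for a joint model, and a real sex difference could be diluted (crude OR about 1.5 for a true 2.0). The age test is affected less. If either condition is absent, the sex test is not distorted.

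These sizes rest on assumed values for the age SD, the age gap, the age gradient and equal numbers of each sex; only n = 200, 15% and alpha 0.05 come from the documents. The documents do not support the stronger readings that the sex result will be spurious or that the crude tests should be withdrawn. The primary prevalence estimate does not depend on this, so it is a minor, cheap improvement to one secondary outcome.

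**What to change.** Add to Section 6 and to the Summary one logistic regression of any AF (present or absent) on age, per 10 years, and sex together. Report adjusted odds ratios with 95% confidence intervals beside the planned chi-square/Fisher and t-test results, which stay as they are. Base any statement about an independent age or sex association on the joint model.

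The document is dated August 2025 and the data window closed in July 2025, so label the model as added after that window.

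The cost is one sentence in each place and one model fit on variables already required at inclusion. The model assumes a linear age effect on the log-odds, and its power for sex is slightly lower than the crude test's when the sexes differ in age but AF does not vary with age. About 30 cases suffice for two terms when the outcome is any AF; modelling complete and incomplete AF separately would leave fewer cases for each.
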